3.1.3 Presentation of results

Tables will present TEAEs and post-treatment AEs only. Pre-treatment AEs will only be listed.

An overview table will show the number and percentage of subjects with at least one event and the number of events by treatment for the following:

- TEAEs
- Serious TEAEs
- Non-serious TEAEs
- ADRs
- Serious ADRs
- Severe TEAEs
- TEAEs leading to study drug discontinuation
- TEAEs leading to death
- Peri-dosing TEAEs
- ADRs leading to study drug discontinuation
- ADRs leading to death
- Peri-dosing ADRs
- Post-treatment AEs

All AEs, including pre-treatment events and all coding information will be listed. AEs started after date of last study medication intake will be flagged. Blank system organ classes and preferred terms, if any will be shown as ‘Not Available’.

3.2 CLINICAL LABORATORY EVALUATION

3.2.1 Available data

Per protocol, the following laboratory parameters are expected:

- Biochemistry: potassium, sodium, magnesium, phosphorus, C-reactive protein, urea nitrogen, calcium, creatinine, glucose, bilirubin (total serum bilirubin), bilirubin (direct or conjugated)
- Hematology: red blood cells count, hematocrit, total hemoglobin, white blood cells count, absolute neutrophils count, neutrophils count %, absolute lymphocytes count, lymphocytes count %, absolute monocytes count, monocytes count %, absolute eosinophils count, eosinophils count %, absolute basophils count, basophils count %, platelets count
- Liver function: alanine aminotransferase (ALT) and aspartate aminotransferase (AST)

Normal ranges are available as provided by the laboratory.

3.2.2 Derivation rules

- The following abnormality categories will be defined:
 - Low: value < lower limit of normal range
 - Normal: lower limit of normal range \leq value \leq upper limit of normal range
 - High: value > upper limit of normal range

Note: classification will be done in standardized units, using non-imputed values and normal ranges.

3.2.3 Presentation of results

The results will be presented in standardized units.

All laboratory data will be listed.

3.3 VITAL SIGNS

3.3.1 Available data

The following vital signs parameters are collected:

- Vital signs: heart rate (HR), respiratory rate (RR), peripheral oxygen saturation (SpO₂), body temperature (BT), systolic (SBP) and diastolic blood pressure (DBP)
- Head circumference, body weight and body length.

3.3.2 Derivation rules

The following vital signs parameters will be derived:

- Head circumference percentile
- Body weight percentile
- Body length percentile

Note: the head circumference, body weight and body length percentiles will be calculated based on the University of Calgary Fenton Pre-term Growth Charts for babies up to 50 weeks of gestational age. If a baby remains in the study beyond 50 weeks of gestational age, the WHO growth standards can be used for the calculation of the percentiles.

- Mean Blood Pressure (MBP) (mmHg) = (SBP + 2 * DBP)/3

3.3.3 Presentation of results

- Vital signs:

All vital signs (HR, RR, SpO₂, BT, DBP, SBP, MBP) data will be listed.

- Head circumference, body weight and body length:

All head circumference, body weight and body length data (including the percentiles) will be listed.

3.4 ESCALATION OF OPIOID WITHDRAWAL

3.4.1 Available data

The following signs of escalation of opioid withdrawal are collected:

- Crying - excessive / continuous
- Persistent inability to sleep
- Tremors and jerks
- Sweating
- Fever
- Mottling
- Nasal stuffiness
- Sneezing
- Poor Feeding
- Regurgitation
- Projectile vomiting
- Loose stools
- Watery stools

3.4.2 Presentation of results

All available information concerning escalation of opioid withdrawal will be listed.

3.5 PHYSICAL EXAMINATIONS

Abnormal physical examination findings will be listed.

3.6 NEUROLOGICAL AND BEHAVIORAL ASSESSMENT

Abnormal neurological and behavioral examination findings will be listed.

4. GENERAL CHARACTERISTICS ANALYSES

4.1 SUBJECT DISPOSITION

The following subject data will be tabulated:

- The number of screen failures overall
- The number of subjects in each analysis set by treatment and overall
- The number and percentage of subjects for each analysis visit included in the list below by treatment and overall
 - Screening
 - Day 1
 - Every 5 days of the treatment phase (Day 5, Day 10, Day 15, ...)
 - Day of last dose
 - End of treatment visit
- The number and percentage of subjects who entered, completed or discontinued each study phase (initiation, escalation, stabilization, weaning and cessation)
- The number and percentage of subjects who completed or discontinued the study as documented on the study termination page and the number and percentage of subjects for each study discontinuation reason by treatment and overall

All information collected in the CRF concerning allocation, code breaking, study discontinuation and information on phases, dates of first signed informed consent, last visit and last contact (over the whole study) and comments will be listed.

4.2 PROTOCOL DEVIATIONS AND ELIGIBILITY

The number and percentage of subjects with major and minor protocol deviations, per category and type, will be tabulated separately, by treatment and overall.

All available information concerning protocol deviations, violations on eligibility criteria (only violated eligibility criteria having DV.DVDECOD = 'VIOLATION OF INCLUSION CRITERION' or 'VIOLATION OF EXCLUSION CRITERION') will be listed.

4.3 DEMOGRAPHIC AND OTHER BASELINE CHARACTERISTICS

4.3.1 Available data

The following parameters will be available:

- Mother demographics: race, ethnicity and maternal characteristics as collected in the eCRF
- Mother drug screen
- Demographics: gestational age, sex, race, ethnicity, date of birth, and date of signing informed consent form (ICF), maternal smoking, alcohol consumption, mode of delivery, family history of prolonged QTc syndrome, unexplained sudden death in otherwise healthy family members and APGAR score
- Screening tests: head circumference, weight, length and vital signs, drug screen
- Baseline characteristics: primary feeding method, feeding type at randomization, maternal primary opioid use (buprenorphine / methadone / other) and use of other licit and illicit drugs, maternal concurrent use of benzodiazepines, antidepressants or gabapentin (polypharmacy)
- Feeding status: nasogastric feed (entire, partial, no), type (maternal breast milk only, formula or donor breast milk, mixed), breast fed (Y/N), estimated volume of maternal breast milk during breast feed (mL), volume of maternal breast milk given by bottle (mL) and volume of formula (mL)
- FNAST scores

4.3.2 Derivation rules

The following vital signs parameter will be derived:

- Mean Blood Pressure (MBP) (mmHg) = (SBP + 2 * DBP)/3

4.3.3 Presentation of results

Mother demographics and drug screen will only be listed.

Demographics will be presented by treatment and overall using descriptive statistics for age, head circumference, weight, and frequency tabulations for sex, race, ethnicity, maternal smoking, and alcohol consumption.

Baseline characteristics (primary feeding method, feeding type at randomization, maternal primary opioid use (buprenorphine / methadone / other) and use of other licit and illicit drugs, maternal concurrent use of benzodiazepines, antidepressants or gabapentin (polypharmacy)) will be presented by treatment and overall using frequency tabulations.

FNAST scores will be summarized by means of descriptive statistics at baseline only (as defined in section 5.2.2) by treatment.

Feeding status will be presented by treatment at Follow-up Day 7, Week 2, and Week 6 using descriptive statistics for estimated volume of maternal breast milk during

breast feed, volume of maternal breast milk given by bottle and volume of formula and frequency tabulations for nasogastric feed, type and breast fed.

In addition, the following parameters will be presented by treatment and overall using descriptive statistics:

- head circumference, weight and length at Screening
- vital signs at Screening

All demographic data, baseline characteristics, feeding status and FNAST scores and screening tests (except when listed in the safety part, i.e. head circumference, weight, length and vital signs) will be listed.

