	
will include treatment (CHF6563 and morphine) as a fixed effect, primary feeding method (formula / any maternal breast milk), maternal primary opioid use (buprenorphine/methadone/other), and concurrent maternal use of benzodiazepines, antidepressants or gabapentin (polypharmacy [yes/no]) as covariates. In cases where observed primary feeding method during the treatment period (formula / any maternal breast milk) differs from the feeding method at time of randomization, the observed primary feeding method will be used for analysis. The adjusted ratio of geometric means between treatments, its 95% CI and associated p-value will be estimated by the model. Babies who discontinue study medication prior to end of the study treatment will be allowed to remain in the study and receive standard of care according to clinical practice. Handling of such cases will be described in the SAP. Babies who discontinue completely (including withdrawal due to treatment longer than 10 weeks) will be imputed using the maximum of the observed value (10 weeks for patients withdrawn due to treatment longer than 10 weeks) or the value of the 90th percentile of duration of any subject completing the study, regardless of treatment group.
 
Secondary efficacy analyses:
 
In cases where observed primary feeding method during the treatment period (formula / any maternal breast milk) differs from the feeding method at time of randomization, the observed primary feeding method will be used for analysis.
 
Time to first weaning (hours) An ANCOVA model based on log-transformed data will be performed to test the treatment effect as time to first weaning (hours). The model will include treatment (CHF6563 and morphine) as a fixed effect, primary feeding method (formula / any maternal breast milk), maternal primary opioid use (buprenorphine/methadone/other), and maternal use of benzodiazepines, antidepressants or gabapentin (polypharmacy [yes/no]) as covariates. The adjusted ratio of geometric means between treatments, its 95% CI and associated p-value will be estimated by the model.
 
Requirement for adjunctive drug therapy (phenobarbital) for signs of NOWS (yes/no) during the treatment period will be analyzed using logistic regression. The Odds ratio and corresponding 95% CI and p-value will be presented, adjusting for primary feeding method (formula / any maternal breast-milk), maternal primary opioid use (buprenorphine/methadone/other), and maternal use of benzodiazepine, antidepressants or gabapentin (polypharmacy [yes/no]).
 
Total hours of treatment with adjunctive therapy will be analyzed using an ANCOVA model. The model will include treatment (CHF6563 and morphine) as a fixed effect and primary feeding method (formula/any maternal breast-milk), maternal primary opioid use (buprenorphine/methadone/other), and maternal use of benzodiazepine, antidepressants or gabapentin (polypharmacy [yes/no]) as covariates. Babies not requiring adjunctive therapy will be included with a value of 0.

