12.3.4 Primary efficacy variable

The primary efficacy variable is the duration of treatment defined as the number of hours from start of the treatment until the last dose of study drug.

An ANCOVA model based on log-transformed data will be performed to test the treatment effect as duration of treatment (hours).

The model will include treatment (CHF6563 and morphine) as a fixed effect and covariates for primary feeding method (formula/ any maternal breast- milk), Maternal primary opioid use (buprenorphine/ methadone / other), and maternal use of benzodiazepines, antidepressants or gabapentin (polypharmacy [yes/no]). In cases where observed primary feeding method during the treatment period (formula / any maternal breast milk) differs from the feeding method at time of randomization, the observed primary feeding method will be used for analysis. The adjusted geometric mean in each treatment group, the adjusted ratio of geometric means between treatments, together with its 95% CI and associated p-value will be estimated by the model.

Missing data handling for the primary efficacy analysis is described in [Section 12.3.2](#).

Sensitivity analyses will be performed as described in the SAP.

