5.2.2 Baseline and change from baseline

The baseline value is a non-missing value before the first administration of any study drug.

Unless otherwise specified, Screening will be used as the baseline measurement. In case there are no assessments/measurements at Screening, the baseline value will be set to missing.

The following table summarizes the baseline definition for each parameter:

Parameter	Baseline
Vital signs	Screening
Head circumference and body weight	Screening
Biochemistry, hematology and liver function	Screening
FNAST scores	Last non-missing value before the first administration of any study drug

Change from baseline is defined as:

Change from baseline at time point t = value at time point t – baseline value.

5.2.3 *Relative day*

Relative days (DY) will be calculated according to the following rule:

- Concerned date < reference date: DY = concerned date – reference date
- Concerned date \geq reference date: DY = concerned date – reference date + 1

The reference date is the date of first administration of study drug

5.2.4 *Analysis visits*

The analysis will use the visits indicated on the subject's CRF. In addition, the vital signs assessments will be allocated to analysis time point windows as defined below based on the actual time of the assessment relative to the first dose (note: time points are not collected on the subject's CRF).

The screening value is the last available and non-missing value before the randomization visit (Day 1). This value corresponds to the screening visit, except in case of retesting. Reason for this approach is the use of retest results for subject eligibility assessment.

Unscheduled assessments will not be used in the analysis unless an unscheduled assessment was done to replace unavailable/unreliable data. The decision whether an unscheduled assessment should be used instead of the original assessment will be taken during the data review meeting before database lock. The selection of the unscheduled assessments to be included in the analysis instead of the original assessments will be done in the corresponding ADaM datasets using appropriate values for AVISIT(N) and ATPT(N). Hard coding (documented in the DRR and by a Note to File signed off by both [REDACTED] and Chiesi Farmaceutici S.p.A) will be implemented in the impacted analysis programs by including a comment.

Baseline is defined in section 5.2.2.

Scheduled and unscheduled assessments will be listed.

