6. CHANGES TO THE PLANNED ANALYSIS

6.1 CHANGES TO THE PLANNED ANALYSIS

A total of 57 subjects were to be randomized in order to obtain 51 evaluable subjects (section 1.4). As only 7 subjects were randomized the study objectives of this study will not be evaluable. No statistical analysis will be performed on the collected data and no data derivation (i.e.: change from baseline) will be defined in the present SAP v2.0 (except for some safety parameters).

For the same reasons the following analysis sets planned in the study protocol, have not been defined in section 5.1.1:

- ITT set,
- PP set.

Duration of breast feeding will not be analyzed as stated in the CTP since these data are not collected at baseline.

The aforementioned changes, further detailed in section 6.3, and described in detail in this SAP (v2.0), will replace the analysis as proposed in the study protocol.

[figure not shown]

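### Does it matter that SAP v2.0 tabulates primary feeding method as a baseline characteristic without saying when or how it is observed?

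*SAP*

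**What the plan says.** SAP 4.3.1 sets out the data to hand and includes "Baseline characteristics: primary feeding method, feeding type at randomization, maternal primary opioid use". SAP 4.3.3 then has these characteristics, in a list that opens "Baseline characteristics (primary feeding method, feeding type at randomization, maternal primary opioid use", tabulated by treatment and overall; the table is 14.1.2.2, on the Safety Set. Feeding type at randomization stands next to primary feeding method, so the SAP treats them as two variables.

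SAP 5.2.2 gives the general rule: "The baseline value is a non-missing value before the first administration of any study drug". SAP 4.3.2, the derivation section for this part, opens with "The following vital signs parameter will be derived" and contains only mean blood pressure.

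On a neighbouring variable, SAP 6.1 says: "Duration of breast feeding will not be analyzed as stated in the CTP since these data are not collected at baseline".

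The protocol uses primary feeding method in two ways. Section 12.3.3 lists it among the demographic and baseline variables. Section 12.3.4 makes it a model covariate and says that where feeding observed in the treatment period "differs from the feeding method at time of randomization, the observed primary feeding method will be used for analysis". The same override stands in 12.3.5 and twice in the protocol outline.

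**The concern.** Read in sequence, these sections suggest that a post-dose variable is labelled as baseline. The SAP defines baseline as pre-dose and removes one feeding variable on that ground. It then keeps another whose only stated time frame in the protocol is the treatment period. The schedules of assessments in both documents add to the doubt, because the first tick for feeding status is in the column running from randomization to stabilization, not at screening.

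There is also a reproducibility worry. Protocol 7.2.2 has feeding recorded daily, so many records must be reduced to one value. The word primary suggests the predominant method, while the level name says any. Two programmers could fill the row differently. In a trial with an efficacy analysis more would be at stake: treatment length is the primary endpoint, so a covariate observed over that same period is not independent of it.

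**Working it through.** No figure in the plan bears on this point, so the check is mainly a comparison of text, followed by the size of the largest plausible error.

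**1. Where the label comes from.** Protocol 12.3.3 names primary feeding method, feeding type at randomization and duration of breastfeeding together in its baseline list. SAP 4.3.1 and 4.3.3 repeat the first two. The tension between baseline and on-treatment therefore lies inside the protocol (12.3.3 against 12.3.4); the SAP inherited it.

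**2. Whether the missing derivation proves a gap.** SAP 4.3.1 places the variable under available data, apart from the longitudinal feeding-status records. A collected item needs no derivation rule. Nor does the lack of a feeding row in the 5.2.2 table tell us anything: that table also has no row for feeding type at randomization, maternal opioid or polypharmacy, and nobody would doubt that those are baseline. Section 4.3.3 is not confined to pre-dose data either, since it also presents feeding status at three follow-up times.

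**3. Whether the categories are ambiguous.** The CRF records "type (maternal breast milk only, formula or donor breast milk, mixed". The analysis levels in protocol 12.3.4 are formula and any maternal breast milk. Protocol 6.5 and SAP 1.5 put combined feeding, for the randomization factor, with maternal milk.

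| CRF type | Analysis level | Basis |
|---|---|---|
| Maternal breast milk only | Any maternal milk | Direct |
| Mixed | Any maternal milk | Protocol 6.5, SAP 1.5 |
| Formula or donor milk | Formula | By elimination: donor milk is not maternal |

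The mapping is settled in substance. What stays open is the window and how daily records are combined over it. The level name points to any maternal milk within the window. On that reading the row differs from feeding type at randomization only for a formula-fed baby who later receives maternal milk, or for a baby whose maternal milk stops before the window opens.

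**4. The largest effect on the table.** SAP 6.1 gives 7 randomized babies. If all were dosed, one baby classified differently moves the overall percentage by 1/7 = 14.3 points. The documents do not give the split by arm. At 2:1 the target is 7 × 2/3 = 4.67 on CHF6563, so I take the nearest whole splits as assumptions:

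- 5:2 gives 1/5 = 20% or 1/2 = 50% within an arm.
- 4:3 gives 1/4 = 25% or 1/3 = 33.3%.

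These look large only because the arms are tiny. In each case the difference is one baby.

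**5. The effect on any inference.** None. SAP 2.2.3 rules out inferential statistics, and SAP 6.1 states that the reduced analysis replaces the one in the protocol. The models that would have used on-treatment feeding as a covariate will not be run.

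**6. Whether a reader can see through the label.** Listing 16.2.4.4 gives baseline characteristics and Listing 16.2.4.8 gives all feeding data, both per baby on the Enrolled Set. The row in Table 14.1.2.2 can be checked baby by baby, and feeding type at randomization is in the same table.

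**The case for a change.** The best case for a change is consistency at almost no cost. The SAP applied a baseline test to duration of breast feeding and not, visibly, to primary feeding method, although both come from the same protocol list. Following the list cannot explain keeping one and dropping the other. Table 14.1.2.2 is one of the few tables still produced, and one line naming the CRF item, or marking the row as on-treatment, would make it reproducible.

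Part of this stands: the SAP does not state the source or window, and a sentence would have been tidier. The inference from the dropped variable is weaker. Dropping duration because it was not collected at baseline fits equally well with the sponsor having checked which feeding items exist at baseline and kept this one. Removing the row would itself depart from protocol 12.3.3 and need its own explanation in SAP 6.1.

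The covariate argument is a fair question about the protocol's efficacy models. Its size depends on how often babies change feeding during treatment, which the documents do not give, so I attach no number to it. It concerns analyses that SAP v2.0 no longer contains.

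**Conclusion.** No change follows. The observation is accurate: the documents describe primary feeding method both as baseline and as observed on treatment, and the SAP does not say which record is used. It is missing detail that analysts can fill sensibly from the protocol's level names, and filling it in writing would gain nothing that matters here. The live consequence is bounded by the row in question, one baby in 7 (14.3 points overall) for each baby classified differently, with no effect on any estimate, test or conclusion.

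This rests on three things: SAP v2.0 is the governing analysis, the per-baby feeding listings are produced as planned, and the arm splits used for scale are assumed. Whether the variable is a collected CRF item could not be confirmed, since neither the CRF nor SAP v1.0 was supplied; the conclusion is the same either way. If the protocol's efficacy models were ever revived, the choice between feeding at randomization and feeding observed on treatment as covariate would need to be examined separately.

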4.4 MEDICAL HISTORY AND CONCOMITANT DISEASES

4.4.1 Available data

Medical history and concomitant diseases findings are coded using the medical dictionary for regulatory activities (MedDRA) into system organ classes and preferred terms. For each finding (MH.MHCAT is 'GENERAL MEDICAL HISTORY'), a start and stop date or ongoing flag is collected.

